Cystic fibrosis (CF) is an inherited lifelong, life threatening disease which can affect multiple organs in the body. The inherited defect affects a cells chloride ion channels leading to thick and sticky secretions. This is highly problematic in the lung where there is an accumulation of mucus, which in turn blocks the airway and leads to increased breathing difficulties. In addition to this, the mucus acts as a rich nutrient source that promotes colonisation by a wide range of bacterial species, such as; Staphylococcus aureus, Pseudomonas aeruginosa and Burkholderia cepacia complex species. As infection and lung damage progress over the years, P. aeruginosa becomes the dominant infective species, accounting for 33% of all UK CF lung infections, with 55% of patients prescribed long term inhaled antibiotics to help try and prevent/remove these infections (ECFSPR Annual Data Report 2013). Long term exposure to antibiotics leads to the emergence of Antimicrobial Resistance (AMR) amongst bacterial cells, which is now recognised globally as one of the major threats to human health. Globally, 700,000 people die each year as a result of AMR, requiring the UK government to develop a 5 year plan in order to combat AMR (O'Neill 2014). The direct effects of AMR are far reaching, resulting in; an inability to control infections (which we once could with the same antimicrobial agents), increased morbidity, increased mortality, and decreased patient wellbeing, all of which lead to increased healthcare costs (Roberts 2009; Romling 2014). The upper respiratory tract (upper airways and sinuses) of CF patients are frequently infected and therefore act as reservoirs of infection for the lower respiratory tract (Johansen 2012). Therefore, we have an urgent need for new and sustainable antimicrobial treatments for those suffering with CF as over 80% of patients will require treatment as a result of chronic infection and subsequent inflammation which ultimately leads to lethal respiratory failure (Lyczak 2002).

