8.1 Inclusion Criteria

The following criteria will be used to determine the eligibility of a patient to participate in the study.

- The patient is willing and able to give informed consent.
- The patient must be \geq 18 years.
- The patient must have an established diagnosis of CF (one or more of the following)
 - Sweat chloride >60mEq/L
 - Presence of two CF causing mutations.
- The patient must have chronic symptoms of rhinosinusitis according to the criteria of the European Position Paper on Rhinosinusitis (appendix A).
- The patient scores greater \geq 7 on their SNOT-22 questionnaire.

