9.1 Recruitment

A member of the clinical research team (as per the delegation of duties log) will identify potential participants when arranging their routine clinic meeting at the AWACFC. As part of the letter sent out informing the patient of their routine clinic meeting, the clinical research team will include a letter, patient information sheet, and patient consent form. This will allow the patient to read through the information prior to attending their routine clinic appointment. During this week period, they are able to call the clinical research team to ask any questions. At the meeting appointment, the patient will have another opportunity to ask questions about the study. These patients will be recruited opportunistically at their meeting if they meet the inclusion criteria without any excluding criteria.

All potential participants will be recruited from the AWACFC during routine clinical meeting. All data gathered during this process will only be seen by the clinical research team whom will also be delivering their standard care, so there should be no issues with confidentiality. This information will be passed onto the academic research team (as per the delegation of duties log) in an anonymised state so as to project the study participant.

Participants will provide answers to a SNOT-22 questionnaire as part of standard practice and if their score meets the inclusion criteria, the clinical research team will discuss the trial in detail with the patient. If the patient is happy to proceed, informed consent will be taken, and the patient will become a participant of the study immediately with all their data being randomised against a participant ID number. As per the patient consent form their GP will be subsequently notified of their involvement in the study. Participants will then be randomly separated into two groups:

- Group 1 Those who will use the standard sinus rinse.
- Group 2 Those who will use the standard sinus rinse with the addition of manuka honey.

During their routine clinic meeting (Visit 1), all participants of the study will provide the following data/samples:

• SNOT-22 questionnaire.

Project Proposal – V6.0 –07/09/2020

- Cystic Fibrosis Quality of life (CFQ-R) questionnaire.
- Clinical Record Form (CRF) data.
- Nasal swab.
- Sputum sample.
- Nasal rinse wash solution.

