9.4 Randomisation, Blinding, and Unblinding

A blocked randomisation list will be generated prior to start of study using the electronic random number generator tool (see below). The participants of the study will not be blinded to the treatment they are receiving because the addition of manuka honey to the sinus rinse is obvious and there is no way to negate this. The academic research team will be blinded to which groups the participants (only identifiable by their participant ID number) are assigned. This information (the group allocations and treatment regimens) will only be made available to the academic research team once analysis of the data begins.

- GraphPad QuickCalcs
 - o https://www.graphpad.com/quickcalcs/randomize1/

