9.5 Baseline Assessments

General information will be collected from participants via the clinical record as will information pertaining to their antibiotic usage, their comorbidities, and more specific cystic fibrosis information as per below:

- Age.
- Sex.
- Height
- Weight.
- BMI.
- Smoking status.
- Antibiotic usage (last three months).
 - IV antibiotics.
 - Oral antibiotics.
 - Nebulised antibiotics.
 - Long term antibiotic usage.
- Co-morbidities.
- Cystic Fibrosis specific information.
 - o SNOT-22 score
 - \circ $\;$ FEV1% score. .
- Is the participant undergoing sinus treatment.
- Is the participant used a nasal spray.
- Is the participant recovering from endoscopic surgery.

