11.1 Adverse Events

An Adverse Event (AE) is any untoward medical occurrence in a trial participant which does not necessarily have a causal relationship with this treatment. An AE can therefore be any unfavourable and/or unintended sign (including abnormal laboratory finding), symptom, or disease. We will therefore record signs of an allergic reaction such as;

- Rashes.
- Hives.
- Itching.
- Red and/or swollen skin.
- Blistered and/or peeling skin
- Wheezing.
- Tightness in the chest or throat.
- Trouble breathing, swallowing, and/or talking
- Unusual hoarseness
- Swelling of the mouth, face, lips, tongue, and/or throat
- Nasal irritation.

The following (see below) may be expected with routine use of a sinus rinse protocol and will therefore be recorded but not reported. May can often be avoided by following the administration instructions in the patient information booklet.

- Temporary increase in nasal congestion (often improves with continued use).
- Ear discomfort whilst rinsing.
- Drainage of leftover solution from the nose after rinsing.
- Accidental ingestion of solution (not recommended but deemed not harmful).

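### Section 11.1 files wheeze, chest tightness, breathing trouble and nasal irritation as allergic signs, with no new-or-worse rule and no item-level baseline, in a trial whose participants know their arm

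*Combined protocol and SAP*

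**What the plan says.** Section 11.1 defines an adverse event broadly, as "any untoward medical occurrence in a trial participant which does not necessarily have a causal relationship with this treatment". It then narrows to one cause: "We will therefore record signs of an allergic reaction such as". The 11 items that follow include wheeze, chest or throat tightness, breathing trouble and nasal irritation. A second list covers effects expected from any sinus rinse, which are recorded but not reported.

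Other sections bear on how that list will work:

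- **Background disease.** Section 3 says CF mucus "blocks the airway and leads to increased breathing difficulties". Section 8.1 makes sinus disease an entry condition: "The patient must have chronic symptoms of rhinosinusitis".
- **Baseline.** Section 9.5 opens with "General information will be collected from participants via the clinical record as will information pertaining to their antibiotic usage". It goes on to co-morbidities, SNOT-22 score, FEV1% and sinus treatment, with no line for the signs listed in 11.1.
- **Capture.** Sections 9.1 and 9.6 ask participants in both groups to note observations in a compliance diary. No structured question about the 11.1 signs is described at either visit.
- **Allocation.** Section 9.4 states "The participants of the study will not be blinded to the treatment they are receiving". Blinding is described only for the academic team. Under 9.1, group 2 alone is "Those who will use the standard sinus rinse with the addition of manuka honey".

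**The concern.** Allergic reaction is the risk that 11.1 singles out, so a reader of the results will want to know whether the honey rinse caused it. Two features of the plan make that hard to answer.

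First, nothing separates a sign that a participant brought into the trial from one that began after rinsing. Section 11.1 does use change-from-usual wording elsewhere: hoarseness must be unusual, and congestion must have increased. Wheeze, chest tightness, breathing trouble and nasal irritation carry no such qualifier. If existing signs are counted, they raise the rate in both arms and leave fewer participants in whom a new reaction can show.

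Second, the signs are labelled allergic before anyone has judged their cause, and participants know whether they are using a bee product. A group 2 participant may be readier to write down a wheeze than a group 1 participant with the same wheeze. That would push the comparison the other way, towards an apparent honey effect.

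This is a pilot meant to inform a larger study, so its tolerability data matter even without a formal test. A Visit 1 record that was never made cannot be reliably recovered later.

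**Working it through.** The plan gives no adverse event rate, count or comparison, so there is no figure of its own to reproduce. The calculations below only show direction and rough scale.

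**Inputs.** The target sample size is 30 (Section 12.2). Allocation of 15 per arm assumes 1:1, because the ratio is not stated. All sign rates and recording probabilities are assumptions.

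**A. Dilution, with equal recording in both arms.** Let *b* be the share with a listed sign at entry. Suppose honey gives a new sign to 20% of those without one, and control gives none.

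- Control rate c = b
- Honey rate h = b + (1 − b) × 0.20
- SE = √[c(1 − c)/15 + h(1 − h)/15]
- z = (h − c)/SE

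| b | c | h | Excess (points) | SE | z |
|---|---|---|---|---|---|
| 0 | 0 | 0.20 | 20 | 0.103 | 1.94 |
| 0.3 | 0.30 | 0.44 | 14 | 0.174 | 0.80 |
| 0.5 | 0.50 | 0.60 | 10 | 0.181 | 0.55 |
| 0.6 | 0.60 | 0.68 | 8 | 0.175 | 0.46 |

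The first z should not be read as near-significance. With an empty cell and 15 per arm the normal approximation is poor. The matching table, 0/15 against 3/15, has a two-sided Fisher p = 2 × C(15,3)/C(30,3) = 2 × 455/4060 = 0.22. The useful column is the excess.

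**B. Unequal recording, with no true honey effect.** Expected count = 15 × background rate × probability that the sign is recorded.

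| Background | Recording, control / honey | Expected control | Expected honey | Difference | P(Fisher p ≤ 0.05) |
|---|---|---|---|---|---|
| 20% | 0.5 / 0.5 | 1.5 | 1.5 | 0 | 0.005 |
| 60% | 0.8 / 0.8 | 7.2 | 7.2 | 0 | 0.016 |
| 20% | 0.5 / 0.7 | 1.5 | 2.1 | 0.6 | 0.012 |
| 60% | 0.5 / 0.7 | 4.5 | 6.3 | 1.8 | 0.042 |
| 20% | 0.5 / 0.9 | 1.5 | 2.7 | 1.2 | 0.028 |
| 60% | 0.5 / 0.9 | 4.5 | 8.1 | 3.6 | 0.140 |

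With equal recording the arms are equal in expectation. The missing baseline rule inflates counts but does not by itself unbalance them. Any imbalance in B comes wholly from the assumed difference in recording.

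**Taken together.** A shrinks a real excess and B enlarges an apparent one. They act in opposite directions, so an observed difference, or the lack of one, could not be attributed with confidence.

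**The case against.** A reader might infer that Visit 1 has no symptom record at all. The documents do not support that. Both arms complete the SNOT-22 and CFQ-R at Visits 1 and 2. Section 10.2 says the first surveys nasal complaints and the second covers symptom difficulties. FEV1% and co-morbidities are also on the baseline list. The full CRF and the procedures document mentioned in Section 9 are not available to check. What remains is narrower: no item-level record of the 11.1 signs is described, the areas named in 10.2 do not include wheeze or chest tightness, and nothing ties either questionnaire to adverse event recording.

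A reader might also infer that counts will be unequal. That is a risk, not a certainty. The 11.1 list and the diary apply to both arms, the definition requires no causal link, and randomisation balances background symptoms in expectation.

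The documentary support for overlap is also limited. Section 3 mentions breathing difficulty, and 8.1 with Appendix A covers chronic nasal symptoms, though Appendix A does not name irritation. That wheeze and chest tightness are also background features is a clinical inference. Rash, hives and facial swelling, counted separately, would not be diluted by background wheeze; the pooled any-sign rate in A is a device for illustration.

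Finally, Sections 4 and 12 contain no adverse event endpoint and no between-arm comparison of events. All these limits stand. None supplies a new-or-worse rule or a matched baseline for the listed signs.

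**Conclusion.** The point holds as a weakness in how safety data are recorded and labelled. It is not an error in a planned result. As written, a recorded wheeze or breathing complaint cannot be reliably classed as old disease or new reaction, and open allocation combined with an allergy label leaves room for unequal reporting. The consequence is confined to the reading of descriptive safety data; no stated objective, endpoint or test changes.

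The size is unknown. On the assumed rates, a 20-point excess falls to between 8 and 14 points when 30% to 60% have a listed sign at entry, and unequal recording produces a spurious excess of 0.6 to 3.6 participants. Both results rest on 1:1 allocation and 15 per arm. The dilution result also assumes no new signs in control, and the second assumes a recording gap for which the documents give no evidence.

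**What to change.** In 9.5, 9.6 and 11.1:

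1. Put the 11.1 signs on one checklist under a neutral title that does not mention allergy.
2. Complete it for every participant in both arms at Visit 1 before the first rinse, and again at Visit 2 with the same questions, whatever the suspected cause.
3. Record every sign. Flag as treatment-emergent those that are new or worse than at Visit 1, with the onset date.
4. Assess attribution as a separate step after recording.
5. Tabulate all signs and treatment-emergent signs by arm, as description only.

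The cost is one extra CRF checklist, a short addition to 11.1 and about a minute more at each of two visits that already take place. Unblinded participants may still answer differently, so the checklist reduces unequal recording but does not remove it.

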11.2 Serious Adverse Events

A Serious Adverse Event (SAE) is any adverse event that meets one or more of the criteria

listed below:

- Results in death
- Is life-threatening
- Requires hospitalisation or prolongs existing hospitalisation
- Results in persistent or significant disability or incapacity
- Results in a congenital anomaly or birth defect
- Other medically important condition

Bwrdd lechyd Prifysgol Caerdydd a'r Fro Cardiff and Vale University Health Board

11.3 Reporting Serious Adverse Events

In the event of a SAE, the study coordination centre will be contacted by phone and then sent a completed SAE form within 24 hours as above. The research team will report all related SAEs as required by their REC and/or R&D Office.

Contact details for reporting Serious Adverse Events (SAEs)				
ATTENTION FOR [name]				
Please send SAE forms to:				
All Wales Adult Cystic Fibrosis Center, University Hospital Llandough,				
[name]				
[contact]	[contact]	(Mon to Fri 09:00 – 17:00)		

All Serious adverse event in studies sponsored by Swansea University must be reported to the sponsor immediately and within 24 hours of the research team becoming aware of the event. Swansea University Research Governance Office should be informed at [contact]"

A serious adverse event (SAE) occurring to a participant will be reported to the REC that gave a favourable opinion of the study by the Principal Investigator (PI; [name]). Reports of related and unexpected SAEs will be submitted to the REC within 15 working days of the PI becoming aware of the event, using the National Research Ethics Service (NRES) report of serious adverse event form (see IRAS/NRES website).

Unrelated and Expected SAEs do not require reporting but a copy of the SAE report should be retained in the study master file for audit purposes by research governance, unless alternative arrangements have been agreed during study set up. The Chief Investigator (CI; [name]) will send the Annual Progress Report (APR) to the main REC and Sponsor using the NRES template.

11.4 Urgent Safety Measures and Serious Breaches of GCP

The CI and PIs may take immediate safety measures to protect research participants against any hazard to their health or safety without prior authorisation from the REC or sponsor, however they must alert the sponsor and CI as soon as possible. The CI will notify the REC of the presenting Project Proposal – V6.0 - 07/09/2020

issue within 3 days of the urgent measure setting out the reasons for the urgent measure and the plan for further action. If a site PI identifies the presenting issue, he or she should also inform their local R&D department.

In the event that a serious breach of GCP is suspected, this will be reported to the Sponsor and REC immediately and will be investigated by the sponsor. Any corrective action required will be undertaken by the CI and REC informed. If necessary, a protocol amendment will be submitted for review.

Bwrdd lechyd Prifysgol Caerdydd a'r Fro Cardiff and Vale University Health Board

12. Statistics and Analysis

12.1 Description of Statistical Methods

Qualitative analysis will include the difference between the SNOT-22 and quality of life questionnaire (CFQ-R) scores being assessed before and after treatment within and between both patient groups (with/without manuka honey). To determine if manuka honey caused a change in the amount/type(s) of bacteria present compared to the control group, a contingency table with odds ratio will be prepared taking into account co variants. Infrared spectra will be baseline corrected and vector normalised. Absorbance from specific infrared wavenumbers representative of mucin glycan molecular structures will be compared against in-house sputum spectral libraries to determine increase or decrease in glycosylation patterns as well as structural changes post-treatment. Comparisons in absorbance at key wavenumbers between groups will be analysed using ANOVA.

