4.1 Primary Objectives

Objective	Outcome Measure / Endpoint	
Does the addition of manuka honey to the sinus rinse impact on the SNOT-22 score of patients with cystic fibrosis?	SNOT-22 scores will be completed before and after the use of a sinus rinse with/without manuka honey.	

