4.2 Secondary Objectives

Objective	Outcome Measure / Endpoint
Does the addition of manuka honey to a sinus rinse alter the quality of life of patients with cystic fibrosis?	Quality of life questionnaires (CFQ-R) will be completed before and after the use of a sinus rinse with/without manuka honey.
Does the addition of manuka honey to a sinus rinse impact on the bacterial type/amount found in the nasal/paranasal cavities of patients with cystic fibrosis?	Swabs, a sinus rinse wash sample and a sputum sample for each participant will be collected before and after the use of a sinus rinse with/without manuka honey. Bacteria amount and types will be analysed in each sample.
Does the addition of manuka honey to a sinus rinse protocol change the structure of sputum mucus in patients with cystic fibrosis?	Sputum samples from each participant will be analysed before and after the use of a sinus rinse with/without manuka honey by fourier transform infrared spectroscopy.

Bwrdd lechyd Prifysgol Caerdydd a'r Fro Cardiff and Vale University Health Board

5. Study Design

This is a single site study to be run at the AWACFC based in University Hospital Llandough (Cardiff and Vale Health Board) when patients attend any routine clinic meeting. The work on site will be carried out by the clinical research team as per the delegation of duties log.

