12.2 Number of Participants

The proposed sample size combines a power calculation and a consideration of logistical constraints. We expect to see 290 patients per year of which 50% should complete a SNOT-22 form. Of the 145 forms received around 72 (50%) should be above average. If we allow for a low recruitment rate (of 30-40%) we believe it is realistic to enrol at least 20-30 patients per year. Over the 18 months of the project we feel, therefore, a sample size of 30-40 can be realistically achieved.

Savastano (2014) published summary details of SNOT-22 scores for CF patients (who should well approximate our sample group) reporting a mean (SD) scores of 30.5(14.5). We draw our definition of a clinically significant change from Hopkins et al (2009), who propose 8.9 points. The study will be structured as a 2-sided equality trial, with before and after measurements for each participant. In order to obtain a power of 80% we would require a sample size of at least 21. We therefore propose that a target sample size of 30, since this will be both achievable and will deliver sufficient power, even allowing for drop outs.

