12.3 Analysis of Outcome Measures/Endpoints

All participant data will be analysed by the academic research team after the end point of the study. The data will be sorted into the two treatment groups before analysis is carried out. The

primary outcome measures will be to determine whether the SNOT-22 score of the manuka honey treatment group has improved compared to the standard treatment. The secondary outcomes will be to see if; the lifestyle questionnaire scores have improved, the amount/type(s) of bacteria has changed, and whether the structure/composition of sputum mucus has changed in the same two groups. If any participants withdrew before the second visit/second set of samples were taken then that data will be excluded from analysis.

Bwrdd lechyd Prifysgol Caerdydd a'r Fro Cardiff and Vale University Health Board

13. Data Management

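### The primary between-arm SNOT-22 comparison has no named test, the within-arm comparisons are not ranked below it, and the visit-1 score is not used as a covariate (free improvement: ANCOVA)

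*Combined protocol and SAP*

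**What the plan says.** Section 4.1 sets the primary objective as a question about the added effect of honey: "Does the addition of manuka honey to the sinus rinse impact on the SNOT-22 score of patients with cystic fibrosis". Section 12.3 states the primary outcome as a comparison of arms: "whether the SNOT-22 score of the manuka honey treatment group has improved compared to the standard treatment".

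The method appears only in section 12.1. The sentence opens "Qualitative analysis will include the difference between the SNOT-22 and quality of life questionnaire (CFQ-R) scores" and continues "being assessed before and after treatment within and between both patient groups (with/without manuka honey". No test, model or effect measure is named for SNOT-22, nothing orders the within-arm and between-arm comparisons, and no visit-1 adjustment is mentioned. The synopsis and section 12.2 do not fill the gap.

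The same paragraph is more definite about secondary outcomes. For bacteria, "a contingency table with odds ratio will be prepared taking into account co variants"; for infrared absorbance, ANOVA between groups.

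CFQ-R shares the unspecified SNOT-22 sentence. Its objective in section 4.2 carries the honey comparator ("Does the addition of manuka honey to a sinus rinse alter the quality of life of patients with cystic fibrosis"), while section 12.3 words it more loosely: "The secondary outcomes will be to see if; the lifestyle questionnaire scores have improved".

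The sample size in section 12.2 is "In order to obtain a power of 80% we would require a sample size of at least 21".

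**The concern.** Only the randomised comparison of arms answers whether adding honey changes SNOT-22. Section 8.2 excludes current rinse users and section 9.1 gives both arms a rinse kit, so each arm may improve for reasons unrelated to honey. If within-arm tests stand beside the between-arm test without rank, a significant fall in the honey arm alone could be read as a honey effect. The plan does not say that it will conclude this way; it simply does not rule it out. Section 9.4 releases the allocations to the academic team when analysis begins, so an unnamed primary method could be chosen with allocation known.

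The second part is lost precision. With about 15 per arm, chance baseline differences are not small. SNOT-22 is recorded at visit 1 for every participant, so adjusting for it needs nothing new. A tighter estimate also serves the pilot's stated purpose of informing a larger study.

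**Working it through.** **Inputs.** SD of scores 14.5, difference 8.9 points, two-sided, 80% power, target N = 30 (all section 12.2); planned range 20 to 40 (synopsis and section 8). Assumed because not stated: alpha 0.05, 1:1 allocation (15 per arm at N = 30), the same SD at both visits, and the visit-1/visit-2 correlation r, shown as a range.

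**The plan's own figure.** A one-group before-after calculation with 14.5 as the SD gives n = [(1.960 + 0.842) × 14.5 / 8.9]² = 20.83, so 21. Comparing scores between two arms doubles this to 41.67, so 42 per arm. With a suitable r, about 21 per arm also follows from two-arm ANCOVA (41.67 × (1 − 0.70²) = 21.3) or change scores (41.67 × 2 × (1 − 0.75) = 20.8). From the stated inputs alone, the match is the one-group calculation.

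**Precision of the between-arm contrast.**
- SD for change scores: 14.5 × √(2(1 − r)).
- SD for ANCOVA: 14.5 × √(1 − r²).
- Variance ratio, ANCOVA to change score: (1 + r)/2, so the large-sample cut is (1 − r)/2.

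Power for 8.9 points at 15 per arm uses the noncentral t with 28 df for change scores and 27 df for ANCOVA. The simulated column estimates the slope in each of 40,000 trials and is the more realistic one.

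| r | SD change | SD ANCOVA | Power, change | Power, ANCOVA (formula) | Power, ANCOVA (simulated) | Variance cut, large sample | Variance cut, simulated |
|---|---|---|---|---|---|---|---|
| 0.3 | 17.16 | 13.83 | 28% | 40% | 38% | 35% | 32% |
| 0.5 | 14.50 | 12.56 | 37% | 46% | 45% | 25% | 22% |
| 0.7 | 11.23 | 10.36 | 55% | 62% | 60% | 15% | 12% |
| 0.8 | 9.17 | 8.70 | 73% | 77% | 75% | 10% | 6% |

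Simulated type I error for ANCOVA was 0.049 to 0.051.

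**95% CI half-width**, t × SD × √(2/15):
- r = 0.5: 10.85 points for change scores, 9.41 for ANCOVA by formula. Using the simulated variance ratio, 10.85 × √0.781 = 9.6.
- r = 0.7: 8.40 against 7.76. Using the simulated ratio, 8.40 × √0.876 = 7.9.

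**Equivalent sample size.** In large samples, 30 participants with ANCOVA match 30 × 2/(1 + r) = 40, 35 or 33 with change scores at r = 0.5, 0.7 or 0.8. With the simulated ratios (30/0.781, 30/0.876, 30/0.937) they match about 38, 34 or 32.

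**Across the planned range** (change score to simulated ANCOVA):
- N = 20: 25% to 31% (r = 0.5), 39% to 42% (r = 0.7).
- N = 40: 47% to 58% (r = 0.5), 69% to 74% (r = 0.7).

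**Chance imbalance.** The visit-1 difference between arms has SD 14.5 × √(2/15) = 5.29 points. A 1-SD imbalance shifts the change-score contrast by (1 − r) × 5.29, which is 2.65 points at r = 0.5 (30% of 8.9) or 1.59 at r = 0.7 (18%). This is the same gain seen from another side, not an addition to it.

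**Unranked within-arm tests.** Take 15 per arm, SD of change 14.5 (assumed) and the same true 5-point fall in both arms. Each paired t-test has power 0.238. Exactly one arm is significant with probability 2 × 0.238 × 0.762 = 0.36, and the honey arm alone with probability 0.18, although honey adds nothing.

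**The case against.** Section 12.3 already fixes the primary contrast as honey against standard, and no section makes a within-arm comparison primary. The natural reading of section 12.1 is a between-arm comparison of change, which uses the visit-1 score and is valid. What remains is precision, in a declared pilot, and its size depends on an r that nobody has supplied. All of that stands, and it is why this is an improvement and not an error. It does not remove the case for naming the test: section 12.2 itself claims sufficient power for a stated difference, and section 12.1 offers more than one comparison.

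For the same questionnaire about a month apart, r = 0.3 may be too low. At 0.7 to 0.8 the simulated gain is about 5 to 3 power points. The CI half-widths and equivalent sample sizes by formula are also slightly favourable to ANCOVA; the simulated ones above are fairer.

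Entry at SNOT-22 of 7 or more narrows the visit-1 spread, and this reduces the gain. If visit-1 scores were normal with mean 30.5 and SD 14.5 before selection, truncation at 7 leaves 80% of the variance. Allowing for slope estimation, power then goes from 38% to 45% (r = 0.5) or from 57% to 61% (r = 0.7), with r the correlation before selection. If only above-average scorers entered (above 30.5), the steps would be 42% to 45% and 60% to 61%. The direction holds; the size may be modest.

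Two further limits are fair. CFQ-R is as unspecified as SNOT-22, so the primary outcome is not alone in this. The one-group basis of the sample size is a separate matter that ANCOVA does not cure.

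**Conclusion.** The point holds. The plan makes the between-arm SNOT-22 comparison primary but names no test for it, leaves the within-arm comparisons unranked, and does not use the visit-1 score as a covariate. ANCOVA should be adopted because it costs almost nothing; the plan is not invalid without it.

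At 15 per arm, with SD 14.5 at both visits and two-sided 0.05, ANCOVA cuts the variance of the contrast by 22% at r = 0.5 and 12% at r = 0.7, relative to an unadjusted change-score test (simulated). The gain is small at r = 0.8 (power 73% to 75%), and smaller where entry selection narrows the baseline spread. At N = 30, ANCOVA does not reach 80% power for 8.9 points at any r up to 0.8.

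**What to change.** In sections 12.1 and 12.3:

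- Make the primary analysis an ANCOVA of visit-2 SNOT-22 on randomised arm and visit-1 SNOT-22, reporting the adjusted honey-minus-standard difference with its 95% CI.
- Label within-arm changes descriptive only.
- Use the same model for each CFQ-R score analysed, list those scores, and bring the CFQ-R wording in section 12.3 into line with the honey comparison in section 4.2.
- State that adjustment does not remove bias from unblinded self-report.

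The cost is a few sentences and one degree of freedom. Sections 9.1 and 9.6 already collect SNOT-22 and CFQ-R at visit 1, so no new data are needed.
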